## 7. DOSING DELAYS/DOSE MODIFICATIONS

No Sn-117m-DTPA dose modification is allowed. Patients will be monitored continuously for AEs throughout the study. Patients must be instructed to notify their physician immediately for any and all side effects. Treatment interval is scheduled every 8 weeks or every 56 days with a window period of +/- 7 days for all time points. If the treatment needs to be delayed due to an adverse event, study drug administration can be delayed up to 8 weeks for recovery, with the following conditions:

- Hematological toxicities must resolve to CTCAE grade 1 or less (or, if abnormal at baseline, not more than one grade above baseline) prior to administration of the next Sn-117m-DTPA dose. In the absence of recovery after 4 weeks, patients are to discontinue further study drug administrations.
- Non-hematological toxicities must resolve to CTCAE grade 2 (gastrointestinal events) or grade 3 (other toxicities) prior to administration of the next dose.
- If patients experience spinal cord compression during the treatment phase, Sn-117m-DTPA administration can continue with up to a 4-week delay if the patient is adequately treated with steroids, local SBRT, or surgery.
- If patients experience traumatic fracture in weight-bearing bones during the treatment phase, the study drug administration should be delayed 4 weeks from the fracture.

As a general approach, it is suggested that all AEs be managed with supportive care when possible at the earliest signs of toxicity.

### 7.1 PRO-CTCAE

PRO-CTCAE data should not be used for determining dose delays or dose modifications or any other protocol-directed action.

## 8. PHARMACEUTICAL AGENT INFORMATION

A list of the adverse events and potential risks associated with the investigational agent administered in this study can be found in Section 10.1.

### 8.1 CTEP IND Agent

#### 8.1.1 Sn-117m-DTPA (NSC 824376)

### **Stannic-117m Pentetate (Sn-117m-DTPA) (NSC 824376)**

**Chemical Name:** Stannic-117m pentetate; Sn-117m-diethylenetriaminepentaacetic acid

**Other Names:** Sn-117m-DTPA

**Classification:** Conversion electron emitting radiopharmaceutical

**Molecular Formula:**  $^{117m}\text{SnHC}_{14}\text{H}_{18}\text{N}_3\text{O}_{10}$  **M.W.:** 508.01 g/mole

**Mode of Action:** Tin binds to bone and especially to hypermetabolic areas in bone, such as bone adjacent to tumor metastases, similarly to calcium. Stannic-117m pentetate produces conversion electrons with finite penetration, to 300  $\mu\text{m}$ , resulting in irradiation of tissues only to that distance, sparing bone marrow and other tissues adjacent to the bone-tumor interface. The isotope also produces gamma radiation, enabling imaging.

**Description:** Stannic-117m pentetate is a ligand metal chelate consisting of the radionuclide Sn-117m in the +4 oxidative state complexed to pentetate (DTPA), the chelating agent. The formulation is prepared using a 20:1 molar ratio of DTPA to Sn. Calcium chloride is added to the formulation as an excipient to combine with 80% of the excess (un-complexed) DTPA present in the formulation to minimize DTPA-related toxicity. Stannic-117m pentetate is a low energy conversion electron emitter with also energy emitted as gamma-radiation. Stannic-117m pentetate has a half-life of 14 days and decays to stable Sn-117.

**How Supplied:** Stannic-117m pentetate is supplied by Serene, LLC and distributed to clinical trial sites by IsoTherapeutics Group, Angleton, TX. under a DCTD, NCI-sponsored IND.

Stannic-117m pentetate will be distributed by IsoTherapeutics Group in single-use vials prepared for the subject's planned dose as a sterile, aqueous solution. The solution has a pH between 3 and 5 and contains the following excipients: calcium chloride and water for injection. The solution may contain sodium chloride for pH adjustment. Vials are shipped in a lead container and transported as a Type A radioactive package according to international transportation guidelines for radioactive materials.

Vials will only be shipped to Authorized Users at appropriately licensed facilities with a Radioactive Materials License approved for medical use of Stannic-117m pentetate.

**Preparation:** Stannic-117m pentetate solution is not to be diluted or mixed with any other solutions. Vials are to be assayed in a Stannic-117m pentetate calibrated dose calibrator that has been calibrated with a NIST traceable Stannic-117m pentetate reference standard. Dose calibrators are to be calibrated at time of commissioning, after any maintenance procedures and at intervals of no greater than one year. Vials are to be assayed immediately prior to and after withdrawal of the subject dose. Record radioactive activity administered according to institutional protocol and on the NCI Drug Accountability Record Form. The actual radioactivity administered must be within the tolerance limits of  $\pm 10\%$  of the calculated radioactivity.

A minimum of three (3) records of Stannic-117m pentetate radioactivity MUST be kept and submitted in RAVE for each individual patient administration: (1) radioactivity at initial dose shipment from IsoTherapeutics, (2) radioactivity upon Site receipt, and (3) radioactivity at Site upon administration to the patient confirmed by radioactivity in the vial measured immediately prior to and after withdrawal of the subject dose.

**Storage:** Store vials at room temperature (between 15-30°C). Store vials in the radiation shielding container until use.

**Stability:** Vials will be labeled with an expiration date, which will be 14 days from the date of calibration prior to shipment.

**Route and Method of Administration:** Visually inspect solution for particulate matter or discoloration prior to administration. Stannic-117m pentetate doses are administered by slow intravenous injection over 10 minutes into a free-flowing IV line containing 0.9% sodium chloride. The intravenous access line is to be flushed with 0.9% sodium chloride after injection of Stannic-117m pentetate. Doses must be administered by Authorized Users in a designated clinical setting licensed accordingly for medical use of Stannic-117m pentetate.

### **Special Handling and Precautions:**

Stannic-117m pentetate (a conversion electron emitting pharmaceutical) should be received, used and administered only by persons authorized to handle radiopharmaceuticals in designated clinical settings. The receipt, storage, use, transfer and disposal of Stannic-117m pentetate are subject to the regulations and/or appropriate licenses of the competent official organization (Nuclear Regulatory Commission or the relevant regulatory authority of an Agreement State). Administration may be associated with potential risks to other persons from radiation or contamination from spills of bodily fluids such as urine, feces, or vomit. Therefore, radiation protection precautions must be taken in accordance with national and local regulations.

Stannic-117m pentetate should be handled by the user in a manner which satisfies both radiation

safety and pharmaceutical quality requirements. Appropriate aseptic precautions should be taken. In keeping with the As Low As Reasonably Achievable (ALARA) principle for minimization of radiation exposure, it is recommended to minimize the time spent in radiation areas, to maximize the distance to radiation sources, and to use adequate shielding.

Any unused drug product or materials used in connection with the dispensing or administration are to be treated as radioactive waste and should be disposed of in accordance with local regulations. Unused doses and waste may be destroyed following applicable agreement state and federal regulations for decay in storage for Stannic-117m pentetate following 10 half-lives.

Radiation protection precautions are to be followed in accordance with national and local regulations. Follow normal working procedures for the handling of radiopharmaceuticals and use universal precautions for handling and administration such as gloves and barrier gowns when handling blood and bodily fluids to avoid contamination.

**Patient Care Implications:** Fertile men study participants and their partners must abstain or use effective contraception (including barrier method) while receiving study treatment and for at least 6 months after the last dose of Stannic-117m pentetate. For at least 10-days after each dose, subjects should avoid close contact with others, should flush toilet several times after each use, and should avoid preparing food for others. Clothing soiled with patient fecal matter or urine should be washed promptly and separately from other clothing.

Provide subject with instructions regarding hygiene precautions to abide by at time of therapy completion in accordance with local institutional policies and guidelines for radiation protection.

## Availability

Sn-117m-DTPA is an investigational agent supplied to investigators by the Division of Cancer Treatment and Diagnosis (DCTD), NCI.

Sn-117m-DTPA is provided to the NCI under a Collaborative Agreement between the Pharmaceutical Collaborator and the DCTD, NCI (see Section 13.5).

### 8.1.2 Agent Ordering and Agent Accountability

**8.1.2.1** Sn-117m-DTPA is supplied by Serene LLC and distributed by IsoTherapeutics under a DCTD, NCI-sponsored IND.

- All requests for Sn-117m-DTPA must be submitted to IsoTherapeutics using the attached order request form attached in **Appendix L**. Complete all requested fields on the order request form. Obtain subject's weight prior to each dose. Requests must be submitted to IsoTherapeutics at least one week in advance of the planned administration date and must be shipped to the authorized facility address as identified on the Site On-Boarding Form and to a site shipping contact as identified on the Site On-Boarding Form. A copy of the completed order request form must be retained as a study record.

- Unused doses are to be accounted for on the NCI DARF. Unused doses may be destroyed following applicable agreement state and federal regulations for decay in storage for Sn-117m-DTPA.

The Authorized User investigator prescribing Sn-117m-DTPA must be registered with CTEP, DCTD through an annual submission of FDA Form 1572 (Statement of Investigator), NCI Biosketch, Agent Shipment Form, and Financial Disclosure Form (FDF), and be designated as such on the Site On-Boarding Form and the Delegation of Task Log.

**8.1.2.2 Agent Inventory Records** – The investigator, or a responsible party designated by the investigator, must maintain a careful record of the receipt, dispensing and final disposition of all agents received using the NCI Investigational Agent (Drug) Accountability Record (DARF) available on the CTEP forms page. Store and maintain separate NCI Investigational Agent Accountability Records for each agent, strength, formulation and ordering investigator on this protocol. **All Shipping Declaration Forms received with the Sn-117m-DTPA shipments are considered IND records and must be retained by the site along with the NCI Drug Accountability Records for the trial.**

#### 8.1.3 Investigator Brochure Availability

The current versions of the IBs for the agents will be accessible to site investigators and research staff through the PMB OAOP application. Access to OAOP requires the establishment of a CTEP IAM account and the maintenance of an “active” account status, a “current” password and active person registration status. Questions about IB access may be directed to the PMB IB Coordinator via email.

### 9. STATISTICAL CONSIDERATIONS

#### 9.1 Study Design/Endpoints

This is a single-arm, open-label phase 2 study to evaluate the efficacy of Sn-117m-DTPA on

sustained pain response in patients with CRPC metastatic to at least two bone sites, with at least one clinically meaningful pain at baseline ( $\geq 4$  on an 11-point pain intensity scale). Sustained pain-response is defined as: 1) achieving pain index  $\leq 3$  within a 12-week period and 2) maintaining that pain index  $\leq 3$  over a 16-week time period (beginning when the pain index  $\leq 3$  is initially achieved). The maximum duration of follow-up required to declare a patient a responder is 28 weeks, representing a patient who initially achieves pain index  $\leq 3$  toward the end of the 12-week period and is followed for an additional 16 weeks to confirm maintenance of pain index  $\leq 3$ .

Eligible patients will be assigned to receive Sn-117m-DTPA at 20 mCi/70 kg (0.28 mCi/kg) every 8 weeks for two cycles. Treatment will last for 16 weeks with two treatment injections given at 8-week intervals. The study utilizes a mini-max Simon two-stage design to assess anti-tumor activity and pain benefit of Sn-117m-DTPA.

Patients are not allowed to receive external radiation within 12 weeks from the start of treatment administration. If their pain index does not reach  $\leq 3$  after 12 weeks, they are not meeting the primary endpoint, and they can then get external radiation for pain control.

The sustained pain response rate under null hypothesis is  $p_0=0.1$  and the alternative hypothesis is  $p_1=0.3$ . The literature on sustained pain-relieving benefit with radiopharmaceutical drugs in prostate cancer with bone metastases is limited. Nilsson *et al.* studied the dose-response relationship and pain-relieving effect of radium-223 (Nilsson *et al.*, 2012). Pain response at Week 8 was seen in 40% of patients. The null hypothesis for sustained pain response in the absence of effective therapy and a strong literature support would assume 10%. We propose that the sustained pain response with Sn-117mDTPA would achieve 30%. Using the mini-max Simon's two-stage design, the total sample size is 25 patients, with 10 patients for the first stage and 15 patients for the second stage. If 1 or 0 patients achieve sustained pain response in the first stage, the study will be stopped early for futility; otherwise the trial continues to the second stage. If 5 or fewer patients achieve sustained pain-response, then no further investigation of the study treatment is warranted. This design has an estimated 5% type I error rate and 80% power. The planned sample size and interim analysis has a 3.28% actual type I error rate and 80.17% actual power. The probability of stopping at the end of the first stage is about 55% under the null hypothesis. Study enrollment will be interrupted for the interim efficacy analysis.

The efficacy primary endpoint will also be summarized by the point estimation of the ORR with the corresponding 95% confidence intervals. Patients who received any amount of study drug will be included in the denominator for the calculation of ORR.

Summary statistics on safety endpoints will be calculated and reviewed at the interim analysis or anytime during the study at the investigator's discretion. If there is statistically significant evidence that the DLT probability exceeds 30%, the study should be suspended for further review. A 95% exact binomial confidence interval will be calculated for the DLT rate. If the observed lower bound of the confidence interval exceeds 30%, we consider it statistically significant evidence that the DLT probability exceeds 30%.

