## 9.4 Analysis of Secondary Endpoints

Secondary endpoints will be summarized depending on data type. Categorical endpoints will be summarized by frequency and percent. Continuous variables will be summarized by mean and standard deviation at each assessment time point. Time-to-event endpoints will be summarized by Kaplan-Meier Methods. Safety and toxicity will be assessed through the frequency and percent of adverse events (AEs), serious adverse events (SAEs), and adverse events of special interests (AESIs). Toxicity will be assessed using Common Terminology Criteria for Adverse

Events v 5.0 (CTCAE). Safety and toxicity will also be assessed by patient-reported outcomes and adverse events (PRO-CTCAE) captured by digital instruments during treatment and 8 weeks after the last injection to monitor for acute toxicity and every 2-4 weeks for 6 months post-therapy for monitoring of long-term toxicity. CTCAE grades for the corresponding time period will be presented in conjunction with PRO-CTCAE scores. PSA and ALP response rates will be calculated for each of the above defined categories with the corresponding confidence intervals. *Post-hoc* analysis on PSA and ALP levels may be conducted to explore possible trends in PSA and ALP levels. Time to the first symptomatic skeletal event will be analyzed using the Kaplan-Meier method. Estimation and confidence intervals for the median time to first symptomatic skeletal event will be provided. Patients who did not have a symptomatic skeletal event will be censored at the last study visit. PFS will be analyzed in a similar manner as the time to first skeletal event. Patients who did not have observed clinical progression will be censored at the last assessment.

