#### 9.4.3 Time to First Symptomatic Skeletal Event

The time from study enrollment to 1) the first use of external-beam radiation therapy to relieve skeletal symptoms, 2) new symptomatic pathologic vertebral or non-vertebral bone fractures, 3) spinal cord compression, or 4) tumor-related orthopedic surgical intervention will be evaluated.

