### **9.6.2 Evaluation of Response**

The Per Protocol Population is defined as all patients who are in the Safety Population and have no major protocol violations that could influence the assessment of efficacy. Efficacy analysis, including the analysis of primary and secondary endpoints (excluding safety and toxicity), will be based on the Per Protocol Population.

Responses to treatment will be evaluated per PCWG3 criteria as described in Section 12.1 (for bone lesions).

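### Time to first symptomatic skeletal event uses the Per Protocol set, from which a patient irradiated in Weeks 0 to 12 can be dropped because he had the event

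*Combined protocol and SAP*

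**What the plan says.** Three statements meet on this endpoint.

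- **Event.** Objective 1.2.4 and section 9.4.3 list four components of a symptomatic skeletal event. One is "the first use of external-beam radiation therapy to relieve skeletal symptoms". Neither place sets a time limit or distinguishes permitted from prohibited radiotherapy.
- **Ban.** Section 9.1: "Patients are not allowed to receive external radiation within 12 weeks from the start of treatment administration". Patients whose pain index has not reached 3 or less after 12 weeks miss the primary endpoint, and "they can then get external radiation for pain control".
- **Analysis set.** Section 9.6.2: "Efficacy analysis, including the analysis of primary and secondary endpoints (excluding safety and toxicity), will be based on the Per Protocol Population". That population is the part of the Safety Population whose members "have no major protocol violations that could influence the assessment of efficacy".

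For the analysis itself, section 9.4 specifies Kaplan-Meier: "Estimation and confidence intervals for the median time to first symptomatic skeletal event will be provided". Its only censoring rule is "Patients who did not have a symptomatic skeletal event will be censored at the last study visit". Neither 9.4 nor 9.4.3 names a different analysis set for this endpoint.

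**The concern.** During the first 12 weeks, the same radiotherapy is both a breach of the protocol and an occurrence of the endpoint. Radiotherapy to painful bone in a bone-pain trial is easily read as a violation that could influence efficacy. If it is classed as major, the patient leaves the analysis because of the outcome being measured. That is selection on the outcome, and it removes early events in particular.

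The trial is open-label and does not define a major violation, so the classification can be made after the event is known. There is no control arm in which the same loss could offset it. At stake is the event-free curve for one secondary objective, which would look better than it was in the patients treated.

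**Working it through.** **Step 1: does the text allow the exclusion?** There are two possible paths for a patient given palliative EBRT at, say, Week 6.

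- He stays in the Per Protocol set. The EBRT is an event at Week 6, and 9.4 censors only patients without an event. The result is correct.
- He is classed as a major violator. He and his event leave the analysis together.

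Nothing in the plan closes the second path. The all-treated statement in 9.1, "Patients who received any amount of study drug will be included in the denominator for the calculation of ORR", covers only that response rate. Section 9.4.2 also removes major deviations from a response denominator, so exclusion for deviations is intended practice here.

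A patient whose EBRT is deferred until after Week 12, as 9.1 allows for non-responders, is not affected: his radiotherapy is permitted and counts as an event on its date.

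**Step 2: effect on the event-free share.** The plan gives no event rate, event count or median for this endpoint, so there is no planned figure to reproduce. The only document input is n = 25 (9.1, 9.2).

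Assume that all 25 are treated, that k of them have early EBRT and are excluded, and that nobody is censored before those events. Let d be the number with an event by time t, including the k.

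- All treated: S(t) = (25 − d)/25
- After exclusion: S(t) = [(25 − k) − (d − k)]/(25 − k) = (25 − d)/(25 − k)
- Ratio: 25/(25 − k)

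| k excluded | Ratio | Week 12 share, all treated* | Week 12 share, after exclusion* |
|---|---|---|---|
| 1 | 25/24 = 1.04 | 24/25 = 96% | 24/24 = 100% |
| 2 | 25/23 = 1.09 | 23/25 = 92% | 23/23 = 100% |
| 3 | 25/22 = 1.14 | 22/25 = 88% | 22/22 = 100% |

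*With no other event or censoring by Week 12.

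Censoring after the excluded events leaves the ratio unchanged, because the later risk sets are the same in both analyses.

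**Step 3: effect on the observed median.** Take the median as the first time S is 0.5 or less, with no censoring before it and all k events earlier than it.

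- 25 patients: S is 13/25 = 0.52 after the 12th event and 12/25 = 0.48 after the 13th. The median is the 13th event.
- k = 1: S is 12/24 = 0.50 at the 12th remaining event, which is the 13th original event. The median does not move.
- k = 2: S is 11/23 = 0.48 at the 12th remaining event, the 14th original. The median moves by one event.
- k = 3: S is 11/22 = 0.50 at the 11th remaining event, again the 14th original. The median moves by one event.

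Under an assumed constant hazard with true median M, the expected gap between the 13th and 14th events, with 12 still at risk, is M/(12 × ln 2). For assumed medians of 6 and 9 months this is 0.7 and 1.1 months.

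For scale, an approximate 95% interval around a 9-month median with all 25 events observed is 9 × exp(±1.96/√25), or 6.1 to 13.3 months. The shift lies well inside it.

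**The case against.** The strongest reply is that harm needs several steps that the plan does not state. A patient must be irradiated despite the ban, with no earlier skeletal event. Someone must class this as major. He must then be dropped from an endpoint that names his radiotherapy as an event. The endpoint text points towards keeping him, since it counts first EBRT without a time limit. This stands: exclusion is possible, not mandatory.

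The ban is also less uniform than 9.1 alone suggests. Section 6.3.1 lists only hemi-body external radiotherapy among treatments not to be used during the treatment period. Section 7 lets dosing continue after cord compression treated with local SBRT, and the compression is itself an event. Section 6.4 does not list palliative EBRT as a reason to stop treatment. This too stands, and it narrows the point to palliative EBRT to painful bone. It also means that two analysts could classify the same radiotherapy differently, which is a reason to settle the rule in advance.

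Finally, one could say that the root problem is the undefined major violation in a single set serving all efficacy endpoints. That is fair, but a general definition that named prohibited radiotherapy as major would make this endpoint worse. It needs its own sentence.

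**Conclusion.** The point holds as a minor one. The stated analysis set can remove a patient because he had the event, and nothing assigns this endpoint another set. After the excluded events the direction is fixed in the drug's favour. The factors of 25/24, 25/23 and 25/22 assume 25 treated and no earlier censoring. How often it would happen is unknown, because the documents give no rate of skeletal events, ban violations or exclusions. The endpoint is secondary and descriptive, and the Simon decision is unaffected.

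Three stronger readings are not supported:

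- **That the plan requires exclusion of irradiated patients.** It neither requires it nor rules it out.
- **That 3.1.5 shows early EBRT to be common,** because it accepts EBRT for bone pain within 4 weeks before study treatment. Exclusion 3.2.4 bars external radiotherapy within 4 weeks before study entry and largely closes that route. What remains is that patients enter with worst pain of at least 4 (3.1.4), and that 9.1 provides for radiotherapy in non-responders. That makes early EBRT plausible but gives no rate.
- **That a definite number of months of bias can be quoted.** Any such figure rests on assumed medians and exclusion rates. A long assumed median gives the largest shifts but would seldom be observed. At 15 months, the share with an event by the 12 months of follow-up in 6.5 is 1 − 2^(−12/15) = 43%, and the 13 of 25 events needed for a median occur in only about 23% of trials, with no earlier censoring.

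**What to change.** State in 9.4.3 and 9.6.2 that:

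1. time to first symptomatic skeletal event is analysed in all patients who received at least one dose, which is the Safety Population already defined in 9.6.1;
2. any EBRT for skeletal symptoms is an event on its date, including in Weeks 0 to 12;
3. such EBRT is never a reason to exclude a patient from this analysis.

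The ban in 9.1 can stay. The cost is two or three sentences, with no new data, no extra table and no change to patient care. It should be written before the data are reviewed, so that it does not look like a choice made with the events known.
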